The first application of the assigned study product will be at the investigational site under the supervision of a trained technician. Subjects will be instructed self-assess the signs and symptoms of cutaneous and ocular irritation they are currently experiencing 1-2 hours after first product application.

Visit 1 and Visit 2 may be combined. If Visit 1 and 2 are not combined, Visit 2 must occur within 7 calendar days of Visit 1. If Visits 1 and 2 are combined, the baseline dermatologist and ophthalmologist assessments and subject self-assessment of cutaneous and ocular irritation will occur before the LAST and any product application. The LAST will be completed at least 30 minutes prior to first product application.

Subjects will be instructed to apply their assigned study product at home again the same evening of their first supervised application and then twice-daily for a total of 21 (+2) days as part of their normal skin care routine. A paper diary will be provided to each subject to record the number of daily applications of product, from first application at site to final application at home. Subjects may also record additional information such as AEs or medications used during the home use period in the provided diary.

The final application of product will be at home on the morning of the final visit (Visit 3).

At Visit 3 (final visit), the dermatologist and ophthalmologist will conduct final assessments of the signs and symptoms of cutaneous and ocular irritation, respectively.

A total dermatologist score will be calculated as the sum of the erythema, dryness, scaling and edema scores for the baseline visit and final visit. The dermatologist will determine whether any subject with an increase in total dermatologist score at final visit versus baseline experienced a clinically relevant positive reaction, or not. Similarly, a total ophthalmologist score will be calculated as the sum of the eczema of the eyelid, conjunctivitis, follicles and chemosis conjunctivae scores for the baseline visit and final visit. The ophthalmologist will determine whether any subject with an increase in total ophthalmologist score at final visit versus baseline experienced a clinically relevant positive reaction, or not.

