4.4 End of Study Definition

A subject will be considered to have completed the study if they complete all phases of the study including the last visit, or the last scheduled procedure shown in the [Schedule of Activities](#).

The end of this study is defined as the date of the last subject's last visit (Visit 3).

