7 DISCONTINUATION OF STUDY INTERVENTION AND SUBJECT DISCONTINUATION/WITHDRAWAL

7.1 Subject Discontinuation/Withdrawal

A subject may withdraw from the study at any time at his or her own request or may be withdrawn at any time at the discretion of the investigator or sponsor for safety, behavioral reasons, or the inability of the subject to comply with the protocol-required schedule of study visits or procedures.

The following circumstances require discontinuation of study product and/or premature subject withdrawal:

- Protocol violation that may impact the subject's safety
- Withdrawal of informed consent
- Subject lost to follow-up
- Unblinding of the subject
- Pregnancy

If a subject is discontinued or prematurely withdraws from the study, the reason(s) for discontinuation or withdrawal and the associated date must be documented in the relevant section(s) of the CRF.

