12.3.1 Primary Analysis(es)

The primary endpoint within each group will be the proportion (number and percentage) of subjects determined by a dermatologist to have a clinically relevant positive outcome for cutaneous irritation after 21 (+2) days of product use, which is defined as an increase in total cutaneous irritation score versus baseline and dermatologist characterization as a clinically-relevant positive outcome at Visit 3 (Final Visit).

This is a non-comparative study and the three, separate, within group assessments will form the primary analysis. No comparison between groups will be made. No formal statistical inference will be performed.

The primary analysis will be performed using the Safety population.

In addition, the individual attribute responses and the total score will be listed for each subject by visit and by treatment group.

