12.3.3 Safety Analysis(es)

Adverse events will be tabulated according to the current version of the MedDRA.

Frequencies and percentages will be presented overall, for each system organ class, and for each preferred term. Summaries of treatment-emergent AEs, treatment-related AEs, AEs leading to discontinuation, and serious AEs will be presented for each of the test products.

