4.3.1 Study Product Compliance and Exposure

Compliance data (based on the subject diary data) will also be summarized for the safety population as the percentage of subjects in each study product who took 80% ~ 120% of the number of prescribed uses of study product (PPD [REDACTED]).

The compliance (%) will be calculated as $[(\text{actual number of study product applications} / \text{expected number of study product applications}) \times 100]$,

Where,

Expected number of study product applications = twice daily application for a total of 21 (+2) days;

Actual number of study product applications = expected number of study product applications – missed study product applications + additional study product applications.

Study product compliance will be listed (PPD [REDACTED]). Supervised product application (subject number, and date and time of the supervised procedure) will also be listed (PPD [REDACTED]).

Also, the number of missed and additional study product application will be summarized in PPD [REDACTED].

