4.4.1.1 Primary Endpoint Definition

The primary endpoint within each group will be the proportion (number and percentage) of subjects determined by the study dermatologist to have a clinically relevant positive outcome for cutaneous irritation after 21 (+2) days of study product use, which is defined as an increase in total cutaneous irritation score at Day 21 (+2) versus baseline and dermatologist characterization of this as a clinically- relevant positive outcome (recorded as Yes/No on in the CRF). It will be presented in PPD by study product and overall.

The dermatologist signs and symptoms of cutaneous irritation total score will be calculated as the sum of the individual cutaneous response attributes (erythema, dryness, scaling, and edema). Additionally the change from baseline in the total score will be summarized by number and percentage of subjects by visit for each study product and overall (PPD).

Calculation of dermatologist assessment of signs and symptoms of cutaneous irritation total score and change from baseline in total score:

The cutaneous irritation total score will be calculated in the following way:

Cutaneous irritation total score = cutaneous response score of erythema + cutaneous response score of dryness + cutaneous response score of scaling + cutaneous response score of edema

Change from baseline in cutaneous irritation total score = total score at day 21(+2) – total score at baseline

Where, the cutaneous response score is described in [Table 4-2](#)

Table 4-2 Dermatological Evaluation

Attribute	Description (Score)				
Erythema	None (0)	Very Slight (0.5)	Slight (1)	Moderate (2)	Severe (3)
Dryness	None (0)	Very Slight (0.5)	Slight (1)	Moderate (2)	Severe (3)
Scaling	None (0)	Very Slight (0.5)	Slight (1)	Moderate (2)	Severe (3)
Edema	None (0)	Very Slight (0.5)	Slight (1)	Moderate (2)	Severe (3)

For example, if the cutaneous response score of erythema = 3, cutaneous response score of dryness = 0.5, cutaneous response score of scaling = 2 and cutaneous response score of edema = 0.5.

Then the cutaneous irritation total score will be:

Total score = 3 + 0.5 + 2 + 0.5 = 6.

In addition, the individual attribute responses, total score, change from baseline, clinical relevance and narratives will be listed (PPD) for each subject by visit and by study product.

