4.6.1 Adverse Events and Serious Adverse Events

All AEs will be reviewed by the Clinical Research Scientist or Designee prior to database lock and will be coded to a system organ class (SOC) and preferred term (PT) using the Medical Dictionary for Regulatory Activities (MedDRA).

AEs will be classified as Skin (Face/Non-Face) and non-skin on the AE page of eCRF.

Treatment emergent adverse events (TEAEs) are defined as new AEs that occur on or after the first treatment application (if this date is missing a suitable alternative will be used eg date of

randomization). Adverse events with an onset date/time prior to the first study product application will be considered as non-treatment emergent.

The following summary tables and listings will be presented by treatment.

- Table of TEAEs by SOC and PT (PPD [REDACTED]).
- Table of TEAEs by Skin(Face/Non-Face)/Non-Skin and PT (PPD [REDACTED])
- Table of TEAEs by SOC, PT and severity (PPD [REDACTED])
- Table of treatment-related TEAEs by SOC and PT (PPD [REDACTED])
- Table of treatment-related TEAEs by Skin(Face/Non-Face)/Non-Skin and PT (PPD [REDACTED])
- Table of treatment-related TEAEs by SOC, PT and severity (PPD [REDACTED])
- Table of treatment-related serious adverse events (SAEs) by SOC and PT (PPD [REDACTED]) [only produced if there are more than 5 SAEs]
- Table of AEs related to COVID-19 by SOC and PT (PPD [REDACTED])
- Listing of all AEs (PPD [REDACTED] for all randomized subjects; PPD [REDACTED] for non-randomized subjects)
- Listing of all AEs related to COVID-19 Subjects (PPD [REDACTED] for all screened subjects)
- Listing of deaths (PPD [REDACTED])
- Listing of non-fatal SAEs (PPD [REDACTED])
- Listing of TEAEs leading to study product discontinuation (PPD [REDACTED])
- Listing of TEAEs classified as skin(Face/Non-Face) (PPD [REDACTED])

In the event that there is nothing to report, a null table or listing will be produced.

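### The primary analysis has no rule for a subject who stops or pauses product because of a skin reaction, recovers and attends Visit 3: she counts as a non-event, and other outputs recover her only in part

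*SAP*

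**What the plan says.** **Endpoint.** SAP 4.4.1.1 sets two conditions. The first is "defined as an increase in total cutaneous irritation score at Day 21 (+2) versus baseline". The second is the dermatologist's Yes/No judgement, which Protocol 12.3.1 describes as "dermatologist characterization as a clinically-relevant positive outcome at Visit 3 (Final Visit". Protocol 4.1 limits who is judged: "The dermatologist will determine whether any subject with an increase in total dermatologist score at final visit versus baseline experienced a clinically relevant positive reaction". Scheduled grading takes place only at baseline and the final visit (Protocol 9.2.1), and data enter by nominal visit (SAP 3.4). The Safety population is everyone randomized with at least one application (SAP 4.1.3).

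**Exposure.** The last application is due at home on the morning of Visit 3 (Protocol 1.1, 4.1, 8.2.5), 2-4 hours beforehand (Protocol 5.5). Subjects are told to contact the site about reactions (Protocol 8.2.5).

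**Stopping.** Protocol 7.1 opens its list with "The following circumstances require discontinuation of study product and/or premature subject withdrawal". The list does not name a skin reaction. Protocol 4.4 says "A subject will be considered to have completed the study if they complete all phases of the study including the last visit", with the last scheduled procedure as an alternative, and sets no explicit exposure condition. Missing data are not imputed (Protocol 12.3.8, SAP 4.4.3). Supportive analyses are marked N/A (SAP 4.4.1.3).

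**Other outputs.** A response that the grading scales can describe is not an adverse event unless it is unusual (Protocol 5.8, 8.3.1, 10.1). Protocol 12.3.3 says that summaries of "AEs leading to discontinuation, and serious AEs will be presented for each of the test products". SAP 4.6.1 plans by-treatment tables of facial-skin treatment-emergent events, but for discontinuation only a "Listing of TEAEs leading to study product discontinuation". Compliance is the percentage of subjects "who took 80% ~ 120% of the number of prescribed uses of study product" (SAP 4.3.1).

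**The concern.** In an in-use tolerance study, stopping the product because it irritates is direct evidence of intolerance. The primary endpoint sees only the skin at Visit 3. A reaction in the first or second week that settles once product is stopped leaves no trace in the primary proportion, and the subject still adds one to the denominator. Her Visit 3 score is present, so the missing-data rule does not apply.

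At stake is the reading against the 10% criterion (Protocol section 3, SAP 1.2), from which each product's tolerability is concluded. The key secondary ocular endpoint is built the same way (SAP 4.5.1.1) and has the same gap.

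**Working it through.** **1. Following one subject through the rules.** Suppose a subject reacts, stops or pauses product, clears, and attends Visit 3 with a total at or below baseline.

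- Numerator: the first condition fails. Under Protocol 4.1 the dermatologist is not asked for a Yes/No, so clinical judgement cannot restore her.
- Unplanned visits: they are allowed (Protocol 1.2), but no rule brings their scores into the endpoint.
- Denominator: one application puts her in the Safety population.
- Blind data review: it may exclude data (Protocol 12.3.5), but no criterion covers this case, and exclusion would not count her as a reaction.
- Sensitivity analysis: the one foreseen in SAP section 4 concerns COVID-19 dropouts.

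She is therefore a non-event. Compared with counting her, the proportion can only fall.

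**2. Where else she may appear.**

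| Output | What it shows |
|---|---|
| Facial-skin event tables and discontinuation listing (SAP 4.6.1) | Only if her reaction was recorded as an adverse event; gradable responses are not, unless unusual |
| Compliance (SAP 4.3.1) | An early stop falls outside the band; a short pause does not |
| Deviations, product end date and duration (SAP 4.1.1, 4.1.2) | The missed use, but not as intolerance |

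Compliance arithmetic, taking 21 days x 2 = 42 expected uses:

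- Stop at Day 4: at most 8 uses, 8/42 = 19.0%, flagged.
- Pause: 80% of 42 = 33.6, so 34 uses are enough. Missing 8 gives 34/42 = 81.0%, not flagged; missing 9 gives 33/42 = 78.6%, flagged. Eight uses are four full days.

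**3. The plan's own figure.** Inputs from Protocol 12.1 and SAP 1.4: n = 45 per arm, true rate p = 0.04, pass if fewer than 10% have events. Since 4/45 = 8.9% and 5/45 = 11.1%, a pass is X ≤ 4.

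P(X ≤ 4) = Σ (k = 0 to 4) C(45,k) p^k (1-p)^(45-k) = 0.9668 at p = 0.04, and 0.9668^3 = 0.9037. Both match the plan.

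**4. Sensitivity.** The documents give no rate for stopping and recovering, so a range is assumed. Let 4% have an event at Visit 3 and a further h stop for a reaction and clear, with the same rates in all arms. The same formula at p = 0.04 + h gives:

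| h (assumed) | Rate if both are counted | One arm passes | All three pass |
|---|---|---|---|
| 0 | 4% | 0.9668 | 0.9037 |
| 2 points | 6% | 0.8690 | 0.6563 |
| 4 points | 8% | 0.7098 | 0.3576 |
| 6 points | 10% | 0.5271 | 0.1465 |

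Under the endpoint as written the first row applies whatever h is. If all 50 per arm (150/3) are assessed, 5/50 = 10.0% still meets a criterion of 10% or less and 6/50 = 12.0% does not. The one-arm figures are then 0.9856, 0.9224, 0.7919 and 0.6161, the same pattern.

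**The case against.** The strongest reply is that the protocol does not leave exposure open. It requires application 2-4 hours before Visit 3, so a subject who has stopped is off protocol. A reader might infer from the endpoint definition that nothing requires use of product at Visit 3; Protocol 5.5 says otherwise. What stands is narrower: the analysis has no rule for subjects who do not meet that requirement.

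A reader might also infer from Protocol 4.4 that anyone who attends the last visit is a completer. The text speaks of completing all phases, or the last scheduled procedure. The point does not depend on this, because the analysis set is the Safety population.

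The pathway is inferred. The list in Protocol 7.1 does not include a skin reaction, and subjects are told to contact the site, not to stop. However, Protocol sections 10 and 10.4 separate stopping product from leaving the study for adverse events, so the case is foreseeable.

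It would be too strong to say that the safety outputs miss her altogether. Facial-skin event tables are planned by treatment, and diary and elicited complaints are assessed as possible adverse events (Protocol 8.3, 8.4). Whether an ordinary erythema or dryness reaction at home becomes an adverse event is left uncertain by the exemption for gradable responses. Nor does the compliance band hide an early stopper; it misses only short pauses, and nothing shows that a reaction would clear within four days.

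Finally, the 10% criterion concerns signs determined by a dermatologist. A stop decided by the subject is a different construct. That is a sound reason to keep any added count supportive.

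**Conclusion.** The point holds as a gap in the analysis rules. A subject who stops or pauses for a skin reaction, clears and attends Visit 3 without a raised total is counted as a non-event, and no planned output reliably counts her as intolerant. The direction is certain: such cases can only lower the proportion. The size is not known. One subject can decide an arm (8.9% against 11.1% with 45 assessed). The fall in the per-arm pass probability from 0.9668 to between 0.8690 and 0.5271 rests wholly on the assumed 2 to 6 extra percentage points.

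A reader might infer that every arm's result will be biased. The documents do not support that: they do not show that such subjects occur in any given arm. The power figure is also correct for its stated inputs.

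Separately, Protocol 12.3.3 promises a per-product summary of adverse events leading to discontinuation, while the SAP plans only a listing. Table 5-1 does not record the change. Counts could be read off the listing, so this is a matter of reconciling the documents.

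This is a cheap improvement worth making. It does not show that the primary endpoint is invalid.

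**What to change.** Keep the primary endpoint and its 10% criterion unchanged.

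- In SAP 4.4.1.3, replace N/A with a descriptive supportive count per product: subjects with a primary event, or who stopped or interrupted product because of a facial skin reaction. Use the primary denominator, show it beside the primary result, and label it as broader than the dermatologist-determined endpoint.
- Add the matching count for eye reactions beside the key secondary endpoint.
- At the existing Visit 3 diary review, record the reason and dates for stopped or missed applications, if the CRF (not among the documents) does not already do so.
- Add the per-product summary of adverse events leading to discontinuation, or record its replacement by a listing in Table 5-1.

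No change to the rules for stopping product is proposed. The cost is at most one CRF item and one or two tables. A supportive figure slightly less favourable than the primary one may also be reported.

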4.4.1.2 Statistical Hypothesis, Model, and Method of Analysis

This is a non-comparative study and the three, separate, within group assessments will form the primary analysis. No formal statistical inference is planned for primary endpoint.

4.4.1.3 Supportive Analyses

N/A

4.4.2 Secondary Endpoint Variables

Secondary endpoint variables are defined in [Section 4.5](#)

4.4.3 Handling of Missing Values/Censoring/Discontinuations

Missing data will not be replaced or imputed. Subjects who withdraw from the study prematurely will be included in analyses up to the point of discontinuation.

4.5 Analysis of Secondary Endpoints

4.5.1 Secondary Endpoints

All secondary analyses will be performed using the safety population and no formal statistical inference will be performed.

4.5.1.1 Secondary Endpoint Variable 1

The key secondary endpoint will be the proportion (number and percentage) of subjects determined by the study ophthalmologist to have a clinically relevant positive outcome for ocular irritation after 21 (+2) days of study product use, which is defined as an increase in total ocular irritation score at Day 21 (+2) versus baseline and ophthalmologist characterization as a clinically-relevant positive outcome (recorded as Yes/No on the CRF). It will be tabulated in PPD [REDACTED] by study product and overall.

The ophthalmologist signs and symptoms of ocular irritation total score will be calculated as the sum of the individual ocular response attributes (eczema of the eyelid, conjunctivitis, follicles, and chemosis conjunctivae). Additionally the change from baseline in the total score will be summarized by number and percentage of subjects by visit for each study product and overall (PPD [REDACTED])

Calculations of ophthalmologist assessment of signs and symptoms of ocular irritation total score and change from baseline in total score:

The ocular irritation total score will be calculated in the following way:

Ocular irritation total score = ocular response score of eczema of the eyelid + ocular response score of conjunctivitis + ocular response score of follicles + ocular response score of chemosis conjunctivae

Change from baseline in ocular irritation total score = total score at day 21 (+2) – total score at baseline.

Where, the ocular response score is described in the [Table 4-3](#)

Table 4-3 Ophthalmological Evaluation

Attribute	Description (Score)				
Eczema of the eyelid	None (0)	Very Slight (0.5)	Slight (1)	Moderate (2)	Severe (3)
Conjunctivitis	None (0)	Very Slight (0.5)	Slight (1)	Moderate (2)	Severe (3)
Follicles	None (0)	Very Slight (0.5)	Slight (1)	Moderate (2)	Severe (3)
Chemosis conjunctivae	None (0)	Very Slight (0.5)	Slight (1)	Moderate (2)	Severe (3)

For example, if the ocular response score of eczema of the eyelid = 0.5, ocular response score of conjunctivitis = 0.5, ocular response score of follicles = 2 and ocular response score of chemosis conjunctivae= 0.5.

Then the ocular irritation total score will be:

$$\text{Total score} = 0.5 + 0.5 + 2 + 0.5 = 3.5.$$

In addition, the individual attribute responses, total score, change from baseline, clinical relevance and narratives will be listed (PPD) for each subject by visit and by study product.

4.5.1.2 Secondary Endpoint Variable 2

The other secondary endpoints will be change from baseline (prior to any product application) in the total subject self-assessment scores for signs and symptoms of cutaneous irritation at 1 to 2 hours after first product application and 21 (+2) days of twice daily product use. It will be summarized by number and percentage of subjects by visit for each study product and overall in PPD.

Calculations of subject self-assessment of sign and symptoms of cutaneous irritation total score and changes from baseline in total score:

Subject self-assessment of sign and symptoms of cutaneous irritation total score = cutaneous response score of redness + cutaneous response score of dryness + cutaneous response score of itching + cutaneous response score of stinging/burning + cutaneous response score of tightness

Change from baseline in subject self-assessment of sign and symptoms of cutaneous irritation total score at 1 to 2 hours = total cutaneous score at 1 to 2 hours – total cutaneous score at baseline

Change from baseline in subject self-assessment of sign and symptoms of cutaneous irritation total score at Day 21(+2) = total cutaneous score at day 21 (+2) – total cutaneous score at baseline

Where, the subject self-assessment of cutaneous response score is described in the Table 4-4

Table 4-4 Subject Self-Assessment Scale for Signs and Symptoms of Cutaneous Irritation

Attribute	Description (Score)				
Redness	None (0)	Very Slight (0.5)	Slight (1)	Moderate (2)	Severe (3)
Dryness	None (0)	Very Slight (0.5)	Slight (1)	Moderate (2)	Severe (3)
Stinging/Burning	None (0)	Very Slight (0.5)	Slight (1)	Moderate (2)	Severe (3)
Itching	None (0)	Very Slight (0.5)	Slight (1)	Moderate (2)	Severe (3)
Tightness	None (0)	Very Slight (0.5)	Slight (1)	Moderate (2)	Severe (3)

The individual cutaneous attribute responses, total score and change from baseline in total score will be listed for each subject by visit and by study product (PPD).

4.5.1.3 Secondary Endpoint Variable 3

The last secondary endpoint will be change from baseline (prior to any product application) in the total subject self-assessment scores for signs and symptoms of ocular irritation at 1 to 2 hours after first product application and 21 (+2) days of twice daily product use. It will be

summarized by number and percentage of subjects by visit for each study product and overall in PPD .

Calculations of subject self-assessment of sign and symptoms of ocular irritation total score and changes from baseline in total score:

Subject self-assessment of sign and symptoms of ocular irritation total score = ocular response score of redness + ocular response score of dryness + ocular response score of stinging/ burning + ocular response score of itching

Change from baseline in subject self-assessment of sign and symptoms of ocular irritation total score at 1 to 2 hours = total ocular score at 1 to 2 hours – total ocular score at baseline

Change from baseline in subject self-assessment of sign and symptoms of ocular irritation total score at Day 21(+2) = total ocular score at day 21 (+2) – total ocular score at baseline

Where, the subject self-assessment of ocular response score is described in [Table 4-5](#)

Table 4-5 Subject Self-Assessment Scale for Signs and Symptoms of Ocular Irritation

Attribute	Description (Score)				
Redness	None (0)	Very Slight (0.5)	Slight (1)	Moderate (2)	Severe (3)
Dryness	None (0)	Very Slight (0.5)	Slight (1)	Moderate (2)	Severe (3)
Stinging/Burning	None (0)	Very Slight (0.5)	Slight (1)	Moderate (2)	Severe (3)
Itching	None (0)	Very Slight (0.5)	Slight (1)	Moderate (2)	Severe (3)

The individual ocular attribute responses, total score and change from baseline in total score will be listed for each subject by visit and by product group (PPD).

